## 6.7. Patient-reported Outcomes

All questionnaires listed on the Table of Events, [Table 5](#) will be completed by subjects using an electronic site pad. The SGRQ, UCSD-SOBQ [REDACTED] questionnaires are incorporated as endpoints in this study to assess the subjects' perception of how IPF affects their quality of life and to measure overall disease burden.

At each visit the subject will complete the SGRQ first, followed by the UCSD-SOBQ [REDACTED] [REDACTED] before any other procedures. The person administering the questionnaires should check for completeness but should never help the subject in choosing a response. Subjects will not have access to any data collected, or the results of the previous questionnaires.

- St. George's Respiratory Questionnaire ([Appendix B](#)): The SGRQ is a quality of life health questionnaire that has been validated in IPF. It consists of 76 items in three domains:
  - Symptoms
  - Activity

– Impact of disease on daily life

A total score is calculated from 0 (no health impairment) to 100 (maximum health impairment). In addition to the total score, there is also a score for each domain: symptoms, activity, and impact which are scored 0-100.

- The University of California San Diego Shortness of Breath Questionnaire ([Appendix C](#)): The UCSD-SOBQ is a 24-item dyspnea questionnaire that asks subjects to rate themselves from 0 (“Not at all”) to 5 (“Maximally or unable to do because of breathlessness”) in two areas: 1) how short of breath they are while performing various activities (21 items); and 2) how much shortness of breath, fear of hurting themselves by overexerting, and fear of shortness of breath limit them in their daily lives (3 items). If the subject does not routinely perform the activity, they are asked to estimate the degree of shortness of breath anticipated. The UCSD-SOBQ is scored by summing responses across all 24 items to form a total score. Scores range from 0 to 120.

## 7. DESCRIPTION OF STUDY TREATMENTS

### 7.1. Description of Investigational Product(s)

CC-90001 will be supplied as film-coated 200 mg tablets by the Sponsor and labeled appropriately as IP for this study.

Applicable doses of CC-90001 will be provided as blinded 32 tablet-count, 16-day blister cards according to local clinical study agreement and in accordance with local guidelines. Please refer to the clinical label for more details on storage condition. CC-90001 is not approved for any indication. CC-90001 can be taken with or without food. The dosing schedule is described in Section 7.2.

### 7.2. Treatment Administration and Schedule

All IP treatment allocation will be handled via interactive web response system (IWRS).

**Subjects are instructed to take 2 tablets once daily, approximately the same time of day, with or without food.**

The IPF study subjects are provided with the following IP treatments:

- **24-week Double-blind, Placebo-controlled Treatment Phase: Baseline (Visit 2) to Week 24 (Visit 9)**

Subjects will receive 2 tablets once daily as follows:

- CC-90001 400 mg PO QD (two 200 mg tablets)
- CC-90001 200 mg PO QD (one 200 mg tablet and one placebo tablet)
- Placebo PO QD (two placebo tablets)

*Note: The first dose of IP is taken on the day of Visit 2 and the last dose of IP is taken on the day of Visit 9.*

- **80-week Active Treatment Extension Phase: Week 24 + 1 Day (Day After Visit 9) to Week 104 (Visit 26E)**

Subjects will receive 2 tablets once daily as follows:

- CC-90001 400 mg PO QD (two 200 mg tablets)
- CC-90001 200 mg PO QD (one 200 mg tablet and one placebo tablet)

*Note: The first dose of IP is taken on the day after Visit 9 and the last dose is taken at Visit 26E.*

At Visit 9/Week 24, all IPF subjects originally randomized to placebo at baseline during the 24-week Double-blind Placebo-controlled Treatment Phase will be re-randomized 1:1 to receive blinded CC-90001 (200 mg or 400 mg PO QD) via IWRS during the 80-week Active Treatment Extension Phase. All subjects originally randomized to CC-90001 (200 mg or 400 mg PO QD) will remain on that same blinded treatment assignment. Subjects begin the blinded-dose active treatment the day after Visit 9 (ie, Week 24 + 1 day). During the 80-week Active Treatment Extension Phase, all subjects not on concurrent protocol-allowable

SOC therapy will have the opportunity, if deemed appropriate by the Investigator, to receive allowed SOC [REDACTED].

The PPF substudy subjects are provided with the following IP treatments:

- **24-week Double-blind, Placebo-controlled Treatment Phase: Baseline (Visit 2) to Week 24 (Visit 9)**

Subjects will receive 2 tablets once daily as follows:

- CC-90001 PO QD (400 mg PO QD [two 200 mg tablets], unless review of benefit-risk favors 200 mg PO QD)
- Placebo PO QD (two placebo tablets)

*Note: The first dose of IP is taken on the day of Visit 2 and the last dose of IP is taken on the day of Visit 9.*

- **80-week Active Treatment Extension Phase: Week 24 + 1 Day (Day After Visit 9) to Week 104 (Visit 26E)**

Subjects will receive 2 tablets once daily as follows:

- CC-90001 PO QD (400 mg PO QD [two 200 mg tablets], unless review of benefit-risk favors 200 mg PO QD)

*Note: The first dose of IP is taken on the day after Visit 9 and the last dose is taken at Visit 26E.*

At Visit 9/Week 24, all PPF subjects originally randomized to placebo at baseline during the 24-week Double-blind Placebo-controlled Treatment Phase will receive blinded CC-90001 (400 mg PO QD, unless review of benefit-risk favors 200 mg PO QD) via IWRS during the 80-week Active Treatment Extension Phase. All subjects originally randomized to CC-90001 (400 mg PO QD, unless review of benefit-risk favors 200 mg PO QD) will remain on that same blinded treatment assignment. Subjects begin the blinded-dose active treatment the day after Visit 9 (ie, Week 24 + 1 day). During the 80-week Active Treatment Extension Phase, the decision for PPF subjects to receive additional treatments for pulmonary fibrosis [REDACTED] is at the discretion of the Investigator.

Blinded IP will be packaged in 32 tablet-count, 16-day blister cards. The 16-day blister cards include IP for two additional days in the event the subject is unable to return for their scheduled visit.

- On Visits 2 and 3, one blister card will be dispensed to the subject. Remaining IP from the blister card issued on Visit 2 will be reissued to the subject along with a new card on Visit 3. The subject should be instructed to finish the remaining IP in the blister card issued at Visit 2 before starting the new blister card issued at Visit 3.
- On Visits 4 to 8, two blister cards will be dispensed to the subject per visit.
- On Visits 9 and 10E, one blister card will be dispensed to the subject. Remaining IP from the blister card issued on Visit 9 will be reissued to the subject along with a new card on Visit 10E. The subject should be instructed to finish the remaining IP in the blister card issued at Visit 9 before starting the new blister card issued at Visit 10E.

- On Visits 11E to 16E, two blister cards will be dispensed to the subject per visit.
- On Visit 17E to 24E, three blister cards will be dispensed to the subject per visit.
- On Visit 25E, two blister cards will be dispensed to the subject.

### **7.2.1. Overdose**

Overdose, as defined for this protocol, applies to protocol-required dosing of the IP (CC-90001) only. Therefore, for a drug to meet the overdose definition it must be both required and an IP. In this study the only required IP is CC-90001 and placebo, hence the overdose definition will apply to only CC-90001 (or matching placebo). Other required or optional non-IP intended for prophylaxis of certain side effects, to treat the disease, etc, are excluded from this definition. Overdose for this protocol is defined as ingestion of > 2 tablets within the same calendar day, whether by accident or intentionally. Adverse Events associated with an overdose must be collected on the Adverse Events page of the CRF for all overdosed subjects, but the overdose itself is not considered an AE.

Detailed information about any CC-90001 overdose in this study, regardless of whether the overdose was accidental or intentional, should be reported on the drug exposure CRF page.

### **7.2.2. Dose Modification/Interruptions**

This is a dose-finding study therefore no dose reductions will be permitted. However, in the event the subject experiences a study drug-related adverse event, a temporary IP interruption for up to 4 days will be permitted anytime during the study. The Sponsor should be notified in advance of the dosage interruption; however, the decision to interrupt IP dosing will be based on the Investigator's clinical judgment. If the subject misses 4 or more consecutive days of dosing, Celgene must be contacted to decide whether dosing should resume or whether the subject should be terminated from the study IP and enter the Post-treatment Observational Follow-up Phase.

If a dose of IP is missed, it should be taken as soon as possible on the same day, provided it occurs within 36 hours of the previous dose. The dose should be skipped if the timing of the dose occurs > 36 hours of the previous dose.

*Note: If the dose is missed for the entire day, the subject should not take an extra dose the next day or take an unscheduled dose.*

#### **7.2.2.1. Dose Interruptions for Planned Surgical Procedures**

It is unknown if CC-90001 affects wound healing in humans. Subjects should interrupt IP 7 to 10 days prior to and restart 7 days after any surgical procedures.

### **7.2.3. Method of Treatment Assignment**

An IWRS will be used to track IP assignments for all subjects and treatment groups through the 24-week Placebo-controlled Treatment Phase and 80-week Active Treatment Extension Phase.

### 7.3. Packaging and Labeling

The label(s) for IP will include the Sponsor name, address and telephone number, the protocol number, IP name, dosage form and strength (where applicable), amount of IP per container, lot number, expiry date (where applicable), medication identification/kit number, dosing instructions, storage conditions, and required caution statements and/or regulatory statements as applicable. Additional information may be included on the label as applicable per local regulations.

### 7.4. Investigational Product Accountability and Disposal

Celgene (or designee) will review with the Investigator and relevant site personnel the process for investigational product return, disposal, and/or destruction including responsibilities for the site versus Celgene (or designee).

### 7.5. Investigational Product Compliance

The Investigator(s) or designee(s) is responsible for accounting for all study IP that is issued to and returned by the subject during the course of the study. Accurate recording of all study drug administration (including dispensing and dosing) will be made in the appropriate section of the subject's CRF and source documents. Study personnel will review the instructions printed on the package with the study subjects prior to dispensing the IP. Investigational product will be dispensed as noted in the Table of Events, [Table 5](#). The subjects will be instructed to return the IP containers, including any unused IP, to the study site at each visit for tablet counts and reconciliation. Subjects will be asked whether they have taken their IP as instructed at each study visit. Any problems with IP compliance will be reviewed with the subject. If the subject misses 4 or more consecutive days of dosing, Celgene must be contacted to decide whether dosing should resume or whether the subject should be terminated from the study IP and enter the Post-treatment Observational Follow-up Phase.

Gross compliance problems (eg, missing 4 or more consecutive days of dosing or taking less than 80% of the doses between study visits) should be discussed with Celgene. Compliance will be categorized into 4 classes: < 50%, ≥ 50% to ≤ 80%, > 80% to ≤ 120%, > 120%.

IP compliance will be calculated at each visit as:

$$\text{Compliance (\%)} = \frac{\text{Number of tablets actually taken between visits}}{\text{Number of tablets that should have been taken between visits}} \times 100$$

## 8. CONCOMITANT MEDICATIONS

Over the course of this study, additional medications may be required to manage aspects of the disease state of a subject, including side effects from treatments or progressive disease. All medications (prescription and non-prescription), treatments, and therapies taken by the subject from Screening throughout his/her entire participation in the study, including those initiated prior to the start of the study, must be recorded on the subject's source document and on the appropriate page of the CRF. The dose, unit, frequency, route, indication, date the medication was started, and date the medication was stopped (if not ongoing) must be recorded.

### 8.1. Permitted Concomitant Medications

#### 8.1.1. Permitted Concomitant Medications Throughout the Entire Study

Subjects may take any medication that is not restricted by the protocol and would not be expected to interfere with the conduct of the study. Chronic medication should be dosed on a stable regimen throughout the study.

- Subjects in the concurrent protocol-allowable SOC therapy group must be receiving the same dose of medication for IPF at least 8 weeks prior to Screening Visit 1 and through Visit 9/Week 24. [REDACTED]
- During the 80-week Active Treatment Extension Phase, all subjects not on concurrent protocol-allowable SOC therapy will have the opportunity, if deemed appropriate by the Investigator, to receive allowed SOC [REDACTED].
- Oral corticosteroid(s) at stable dose  $\leq 12.5$  mg/day prednisone or equivalent will be permitted throughout the study. Inhaled corticosteroids at approved doses will be permitted throughout the study.
- The following commonly used products are acceptable for use during the study: acetaminophen ( $\leq 3$  grams/day), ibuprofen, naproxen sodium, NSAIDs, loratadine, pseudoephedrine, guaifenesin, calcium, histamine-receptor antagonists, proton-pump inhibitors, antidepressants, and hypertension drugs.
- Supplemental oxygen is permitted as indicated (eg, new or worsening SOB, etc).
- Subjects may take statins (HMG-CoA reductase inhibitors) on the study however will require careful monitoring. To ensure the safety of the subjects, statins will be dose adjusted to an appropriate therapeutic level while being taken during the study (Section 8.2.1).
- Bronchodilators:
  - Short-acting bronchodilator may be used provided it does not occur within 8 hours of the study visit.
  - Inhaled long-acting bronchodilator may be used provided it does not occur within 24 hours of the study visit

- All medications required to treat adverse events or medical emergencies that occur throughout the study are permitted (eg, antibiotics).

### 8.1.2. Permitted Medications to Treat New or Worsening Shortness of Breath

Medications, such as prednisone (> 12.5 mg/day or equivalent), azathioprine, and cyclophosphamide can be initiated or increased at Investigator's discretion for the treatment of an exacerbation. Subjects may be given supplemental oxygen to alleviate hypoxemia. These drugs should be discontinued at the Investigator's discretion upon resolution of the exacerbation. If an exacerbation has not improved within 6 weeks or a subject has shown signs of further clinical decline despite adequate treatment, the subject should be discontinued from study IP and enter the Post-treatment Observational Follow-up Phase, as per the Table of Events, [Table 5](#).

### 8.1.3. Permitted Concomitant Medications Only During the 80-Week Active Treatment Extension Phase

For subjects not in the SOC group, an antifibrotic therapy that is considered by the country/Investigator as SOC [REDACTED] will be permitted after Week 24 [REDACTED].

## 8.2. Medications that Require Careful Monitoring

High doses of CC-90001 may moderately induce CYP3A4. Subjects receiving drugs that utilize this enzyme in their metabolic pathway (eg, warfarin) should be closely monitored during co-administration. All subjects receiving vitamin K antagonists (eg, warfarin) should be carefully monitored for changes in INR.

CC-90001 may inhibit the transporters P-gp, BCRP, OAT3, OATP1B1, OATP1B3, and OCT2 [REDACTED]. Drugs considered to be substrates of these transporters should be closely monitored for potential drug interactions while subjects are participating in the study. Additional substrates of these transporters can be found in [Appendix H](#). Questions regarding potential co-administration of CC-90001 and drugs that are substrates for these transporters should be discussed with the Sponsor.

### 8.2.1. Statins

Due to the potential for DDIs, the following must be done to ensure the safety of subjects taking statins while on the study:

- During the Screening phase of the study, all subjects receiving statins should be prescribed the lowest approved statin dose for adults approximately 1 week before Visit 2 (Baseline). For example, a subject receiving atorvastatin 20 mg during the Screening Period should be instructed to begin taking atorvastatin 10 mg, instead, approximately 1 week prior to randomization.

*Note: Subjects who are already receiving the lowest approved statin dose for adults should remain on that dose.*

- At Visit 2 (Baseline), eligible subjects will begin treatment with CC-90001. Following multiple oral doses of CC-90001, the steady state should be achieved on approximately Day 5.
- At Visit 3, the lipid profile will be assessed. Based on results of the subjects' lipid profile at Visit 3, the statin dose may be increased to the next highest approved dose, if indicated.

*Note: If the lipid profile at Visit 3 is comparable to the lipid profile from Visit 1 (Screening), the statin dose should not be increased.*

- At Visit 4, the lipid profile will be assessed. Based on the subjects' lipid profile at Visit 4, the statin dose may be increased to the next approved dose, if indicated.

*Note: If the lipid profile at Visit 4 is comparable to the lipid profile from Visit 1 (Screening), the statin dose should not be increased.*

The Investigator should use his/her clinical judgement to decide when/if the further increase in the statin dose is warranted and how to assess these subjects. **In particular, Investigators should monitor closely for AEs associated with increased statin exposures (eg, myalgia, liver function test abnormalities).** If needed, the Investigator should refer the subject to his/her general practitioner or other appropriate healthcare provider for further follow-up.

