Following an initial screening at Visit 1, eligible IPF subjects will be randomized to receive either CC-90001 200 mg or 400 mg PO QD or matching placebo beginning on Day 1 (Baseline [Visit 2]) of the study. At Week 24, all subjects originally randomized to receive placebo will be re-randomized 1:1 to blinded CC-90001 (200 mg or 400 mg PO QD) via interactive web response system (IWRS). All IPF subjects originally randomized to CC-90001 (200 mg or 400 mg PO QD) will remain on that same blinded treatment assignment during the 80-week Active Treatment Extension Phase. During the 80-week Active Treatment Extension Phase, all subjects not on concurrent protocol-allowable SOC therapy will have the opportunity, if deemed appropriate by the Investigator, to receive allowed SOC [REDACTED].

An interim analysis will be conducted when approximately 50 non-SOC IPF subjects have completed 24 weeks of treatment. If the safety and efficacy of CC-90001 are favorable, a separate [REDACTED] substudy in subjects with progressive pulmonary fibrosis (PPF) will be initiated (refer to Section 3.1.1).

A second interim analysis is planned after approximately 40 SOC IPF subjects have completed 24 weeks of treatment. The purpose of the additional interim analysis is to evaluate safety, tolerability and efficacy of CC-90001 in SOC IPF subjects, along with all study subjects enrolled into the study, and to determine if any treatment group should be discontinued.

All subjects who complete the study treatment phases and those subjects who discontinue investigational product (IP) prior to the completion of the study will participate in the 4-week Post-treatment Observational Follow-up Phase.

To ensure the safety of all subjects in the study, the external Data Monitoring Committee (DMC) and SMT will review safety data as described in the DMC charter and SMT plan. Close monitoring of safety data for all subjects will be conducted throughout the study and will include, but not be limited to, labs, ECGs, pulmonary function testing, and adverse events.

The blind should be maintained for persons responsible for the ongoing conduct of the study from first subject enrolled through last subject/last visit of the 4-week Post-Treatment Follow-up Phase of the study. Blinded persons may include but are not limited to: Clinical Research Physician, Clinical Research Scientist, Clinical Trial Manager, Study Statistician, Data Manager, Programmers, Clinical Research Associates.

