### 3.1.1. Progressive Pulmonary Fibrosis Substudy

The exploratory substudy is a Phase 2, multicenter, multinational, double-blind, randomized, placebo-controlled study evaluating the efficacy, safety, [REDACTED] of one PO treatment dose regimen of CC-90001 (400 mg QD, unless review of benefit-risk favors 200 mg PO QD), compared with placebo, for an initial 24 weeks of treatment, in subjects with PPF. This substudy will also assess the efficacy and long-term safety in the 80-week Active Treatment Extension Phase when all PPF subjects will receive CC-90001. [REDACTED]

[REDACTED] This PPF substudy allows non-SOC subjects who were screened and did not receive a confirmed IPF diagnosis following central reading of HRCT and lung biopsy, if obtained, to be considered for the substudy. Enrollment into this substudy will not begin until after the first interim analysis and confirmation is received from the DMC that the overall main study in IPF subjects should continue as planned (Section 9.8).

Approximately 45 non-SOC subjects qualifying for enrollment into the substudy will be randomized in a 2:1 ratio (approximately 30 subjects in the CC-90001 arm and approximately 15 subjects in the placebo arm), for an initial 24 weeks. Subjects who enter and complete the 80-week Active Treatment Extension Phase will receive treatment for a total of 104 weeks. Refer to [Figure 2](#) for the PPF substudy design and [Section 4.2.2](#) for specific inclusion criteria.

[figure not shown]
Following an initial screening at Visit 1, eligible PPF subjects will be randomized to receive either CC-90001 or matching placebo beginning on Day 1 (Baseline [Visit 2]) of the study. At Week 24, all subjects originally randomized to receive placebo will receive CC-90001. All subjects originally randomized to CC-90001 will remain on that same blinded treatment assignment during the 80-week Active Treatment Extension Phase. The decision to receive additional treatments for pulmonary fibrosis [REDACTED] during the 80-week Active Treatment Extension Phase is at the discretion of the Investigator.

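### The statin step-down in Section 8.2.1 is tied to Visit 2, so placebo subjects above the lowest statin dose start CC-90001 after Visit 9 without it

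*Combined protocol and SAP*

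**What the plan says.** Section 1.7 warns that CC-90001 may inhibit liver transporters and BCRP and so raise statin concentrations. Section 8.2.1 gives the response, introduced by "the following must be done to ensure the safety of subjects taking statins while on the study". Its steps are:

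- During Screening, about 1 week before Visit 2, statin users go to the lowest approved adult dose.
- Then "At Visit 2 (Baseline), eligible subjects will begin treatment with CC-90001", and "the steady state should be achieved on approximately Day 5".
- At Visit 3, depending on lipids, "the statin dose may be increased to the next highest approved dose, if indicated". Visit 4 repeats this step. No increase is made if lipids are comparable to Screening.
- After that, "The Investigator should use his/her clinical judgement to decide when/if the further increase in the statin dose is warranted", with close watch for myalgia and liver test abnormalities.

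Section 8.2.1 does not mention placebo, Visit 9 or the extension phase. Sections 1.7 and 8.1.1 promise statin dose adjustment but send the reader to 8.2.1 for the detail.

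For IPF, Section 3.1 says "At Week 24, all subjects originally randomized to receive placebo will be re-randomized 1:1 to blinded CC-90001". For the substudy, Section 3.1.1 says "At Week 24, all subjects originally randomized to receive placebo will receive CC-90001". Section 7.2 puts the first extension-phase dose on the day after Visit 9.

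**The concern.** The protocol chose a preventive dose reduction before first exposure, with monitoring on top. That reduction comes at the right time only for subjects who receive CC-90001 at Visit 2. For the placebo arm it comes 24 weeks early and can be undone before the drug is started.

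Placebo subjects may also be the more likely to be titrated up. If CC-90001 raises statin exposure, it partly offsets a lower statin dose. Placebo gives no such offset, so lipids may drift above Screening and an increase may be indicated. This is an inference from the protocol's own premise, not something the documents report.

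What is at stake is individual safety and attribution of events. The chemistry panel in Section 6.1 lists no creatine kinase, so muscle toxicity would be picked up from symptoms. Under Section 11.2 a confirmed ALT or AST above 3 x ULN ends investigational product without re-challenge. An avoidable statin-related rise could therefore cost a subject treatment and be read as a CC-90001 liver signal.

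**Working it through.** The plan states no figure on this point, so there is none to reproduce. The check has three parts.

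**1. Timing by arm**

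| | Active arms | Placebo arms |
|---|---|---|
| Statin step-down | about 1 week before Visit 2 | about 1 week before Visit 2 |
| Increases allowed | Visits 3, 4 and later, on CC-90001 | Visits 3, 4 and later, on placebo |
| First CC-90001 dose | Visit 2 | day after Visit 9 |
| Step-down required before first dose | yes | none at Week 24 |

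Placebo subjects who stay on the lowest dose throughout are not affected. Those raised during the 24 weeks, or started above the lowest dose after Baseline, are.

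**2. How many**

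From the documents: 55 IPF placebo and 110 IPF active subjects (Section 3.1); about 15 PPF placebo and 30 PPF active (Section 3.1.1). The documents give no rates for the rest, so these are assumptions: statin use 30% to 60%; 80% to 100% of placebo subjects reach Week 24; 25% to 75% of placebo-arm statin users are above the lowest dose at Visit 9.

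Affected = placebo subjects x retention x statin use x share above lowest dose.

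- IPF: 55 x 0.8 x 0.3 = 13.2 to 55 x 1.0 x 0.6 = 33 statin users at Week 24. Affected: 13.2 x 0.25 = 3.3 to 33 x 0.75 = 24.75.
- PPF: 15 x 0.8 x 0.3 = 3.6 to 15 x 1.0 x 0.6 = 9 statin users. Affected: 3.6 x 0.25 = 0.9 to 9 x 0.75 = 6.75.

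As a share of the CC-90001 exposure-period safety summary (Section 9.7), counting all active subjects plus placebo subjects who cross over:

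- IPF: 3.3/(110 + 44) = 2.1% to 24.75/165 = 15%.
- PPF: 0.9/(30 + 12) = 2.1% to 6.75/45 = 15%.

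Increases are optional and barred when lipids match Screening, so the share above the lowest dose could be lower. At 10%:

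- IPF: 13.2 x 0.1 = 1.3 to 33 x 0.1 = 3.3, or 0.9% to 2%.
- PPF: 3.6 x 0.1 = 0.36 to 9 x 0.1 = 0.9, or 0.9% to 2%.

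**3. Timing of a step-down at Visit 9**

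Take Visit 9 as day 0. The first CC-90001 dose is on day 1. Steady state is on about the fifth day of dosing, so about day 5. Visit 10E is day 7 (4 to 10 with the 3-day window) and Visit 11E is day 28 (25 to 31). Both visits already carry the chemistry panel, which includes lipids, ALT and AST. Section 6.2 places evaluations before dosing on the visit day, so Week 24 lipids would still reflect the previous statin dose.

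**The case against.** The case on the other side is that this is an editorial matter. Nothing bars an Investigator from lowering a statin at Visit 9. Section 8.1.1 speaks of dose adjustment throughout the study, Section 8.2 has transporter substrates watched throughout and questions sent to the Sponsor, and every Investigator knows that everyone continuing past Visit 9 takes CC-90001. Visit 10E mirrors Visit 3, chemistry is drawn at Weeks 25 and 28, and Section 11.2 interrupts dosing on raised transaminases. The protocol also accepts statin doses above the lowest alongside CC-90001 in the active arms. No interaction size is visible, and the counts rest on assumed rates.

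Much of this stands. Surveillance after the switch is real, discretion exists, and the upper end of 25 IPF subjects needs full retention, 60% statin use and 75% up-titration together. None of it supplies the missing step. Section 8.2.1 presents its steps as mandatory and prompts only increases. In the active arms, increases follow lipid checks made on CC-90001; in the placebo arm they come before any exposure. A blinded Investigator cannot single out new starters, so a targeted reduction is not possible without a rule covering all arms.

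**Conclusion.** The concern holds. A site following the protocol exactly would omit the plan's own preventive step for any placebo subject above the lowest statin dose at Visit 9. This is a low to moderate safety correction that should be made. The number affected is unknown and probably small: 3 to 25 IPF and 1 to 7 PPF subjects under the stated assumptions, or 1 to 3 IPF and 0 to 1 PPF at a 10% share. The clinical size of the interaction cannot be judged from the documents. The 24-week placebo-controlled comparison is untouched, and the exposure-period safety summary is descriptive, with no inferential testing (Section 9.7).

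**What to change.** Amend Section 8.2.1 in three places:

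- In all arms, so that the blind is kept, any statin user above the lowest approved dose returns to it at Visit 9, after the Week 24 blood draws and before the first extension-phase dose.
- Allow lipid-guided increases at Visits 10E and 11E from the scheduled chemistry. Visit 11E is the firmer point: Visit 10E lipids come only 4 to 10 days after the reduction, whereas Visit 3 lipids come about 2 weeks after the Screening step-down.
- Change the Visit 2 sentence to say that eligible subjects begin blinded investigational product.

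The cost is amended wording and one site instruction at Visit 9, with no new visits or blood draws. There are two downsides. Active-arm statin users above the lowest dose would have an unneeded reduction of about 1 to 4 weeks, longer if several dose steps are needed. Their number is unknown. The ceiling, taking every active-arm subject at 60% statin use, is 110 x 0.6 = 66 IPF and 30 x 0.6 = 18 PPF. Also, the lead before the first CC-90001 dose is 1 day rather than about 1 week, though the reduction still begins about 5 days before the stated steady state. Stepping down a week before Visit 9 would restore the longer lead, but it would need an instruction between visits and would alter the Week 24 lipid results.
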